6.2 Treatment Misallocation

In case of deviation between the as-randomized treatment and the treatment actually received, the treatment actually received will be used in the safety analyses (i.e. an as-treated analysis will be performed). The following rules will be applied in the construct of the populations:

- Subjects randomized but not treated will be excluded from the Safety, ITT and PP populations.
- Subjects treated but not randomized will be excluded from the ITT and PP populations, given there will be no randomized treatment. These subjects will be summarized based on the treatment they received and will be counted in the Safety population.
- Subjects who were randomized, but took the incorrect study drug for the duration of the study, will be summarized based on their randomized treatment for the ITT population and excluded from the PP population. These subjects will be summarized based on the treatment that they received for the safety analyses.

- Subjects who were randomized, but took the incorrect study drug for part of the study (e.g. the subject began the study by taking the incorrect study drug at Visit 2 but switched to randomized study drug at Visit 3) will be discussed during the Blind Data Review Meeting, agreed prior to unblinding, and documented in the Data Review Report prior to unblinding.

6.3 Subgroup Definitions

There are no specific subgroups that are planned for analysis.

7 Definition of Time Points and Analysis Variables

7.1 Definition of Time Points

Start/End of the Randomized Treatment Period

Since many algorithms used in the statistical analyses require the start and/or the end of the randomized treatment period to be identified, ad-hoc variables specifying these dates will be defined. The date of start/end of randomized treatment period will be set according to the following rule:

- The date of **Start of the Randomized Treatment Period** should coincide with the date of Visit 2, the randomization date and the date of first randomized study drug intake. However, discrepancies between these dates may arise and the most appropriate date to be used in such situations requires a case-by-case evaluation. The date of the start of the randomized treatment period will be initially set equal to the date of first randomized study drug intake for all subjects. The need for deviations from this rule in single cases will be evaluated during the data review and documented in the Data Review Report. As a consequence, the distinction between diary data from the run-in and the treatment period will not be based on the EPOCH variable included in the SDTM datasets, but on the algorithms defined in the SAP.
- If Visit 4 or Early Termination visit was completed, then the date of **End of the Randomized Treatment Period** will be defined as Date of Visit 4/ Early Termination Visit. Otherwise, the date of End of Randomized Treatment Period will be defined as the maximum of [Date of Last Study Drug Intake, date of last clinic visit during treatment period (excluding Visit 5 and any unscheduled visits after last dose)].

Period durations (days)

Day 1 is defined as the date of the first dose of randomized study drug. The day prior to Day 1 is Day -1. There is no Day 0.

Periods used in the analysis of this study are:

- Run-in Period: Morning of Visit 1 through the evening of the day before the date of Start of the Randomized Treatment Period.
Run-in duration = date of the day before the date of the Start of the Randomized Treatment Period – date of Visit 1 + 1 day
- Treatment Period: (End of the Randomized Treatment Period minus Start of the Randomized Treatment Period) + 1 day

Inter-visit periods will be used in the analysis of the average number of rescue medication, the percentage of rescue medication-free days, the percentage of asthma symptoms-free days and of asthma control day, the daily asthma symptoms scores and the morning and evening average pre-dose PEF. The periods used in these analyses are:

- Run-in Period: The Run-In Period starts at Visit 1 and runs through morning assessment of the date of Start of the Randomized Treatment Period.

- Inter-visit Period 1: Inter-visit Period 1 starts on the evening assessment of the date of the Start of the Randomized Treatment Period and runs through the morning assessment on the date of Visit 3. If the subject withdraws prematurely after Visit 2 and before Visit 3 any value collected from Visit 2 until the End of the Randomized Treatment Period will be considered for the Inter-visit Period 1. By default Inter-visit Period 2 is missing.
- Inter-visit Period 2: Inter-visit Period 2 starts on the evening assessment of the day the subject returns to the clinic at Visit 3 and runs through the morning assessment of the date of Visit 4.

If the subject withdraws prematurely after Visit 3 and before Visit 4 any value collected from Visit 3 until the End of the Randomized Treatment Period will be considered for the Inter-visit Period 2.

Date of first/last study drug intake

Date of first randomized study drug intake is derived as the minimum of 'Date/Time of administration' between the 4 inhalations (puffs) of the Morning Dose collected on the 'Study drug administration at the clinic' eCRF page. While subjects randomized to open-label QVAR® will only receive 1 inhaler, patients are required to take 2 inhalations of the content of 1 inhaler on site, the morning of Visit 2. For these patients, no minimum is required, since only 1 time is recorded.

Note: The date and time of drug administration at each visit are mandatory variables to be reported in the CRF; no missing or partial data can be accepted. Only CRF data will be considered for the date of first randomized study drug intake.

Date of last randomized study drug intake is derived as 'Date/Time of last intake of study drug' variable collected on the 'Study Termination form' eCRF page. If the date of the last intake of study drug is missing or partially missing, but the date of at least one dose of the study drug is recorded in the diaries or at the clinic, the date of the last randomized study drug intake will be imputed using the following rule:

max [date of last study drug intake in the diaries, date of last study drug intake at the clinic visits]

The need for deviations from these rules in single cases will be evaluated during the data review and documented in the Data Review Report.

Time to discontinuation from the study

Time to discontinuation/completion will be calculated for all randomized subjects, including subjects who complete the study. For subjects randomized but not treated, the time to discontinuation from the study will be imputed as 0. Subject disposition data will be collected on the 'Study Termination form' eCRF page, which provides information about study completion status of a subject. Study discontinuation is recorded along with the main reason for withdrawal. The primary reason for discontinuation could be for lost to follow up or early withdrawal. Patients completing the study will be censored at the Date of Completion. Patients

lost to follow up will be considered as having an event at the date of Discontinuation recorded on the 'Study Termination' eCRF page.

The time to completion/discontinuation from the study (weeks) is defined as:

$$(\text{date of completion/discontinuation} - \text{date of start of randomized treatment period}) / 7$$

Baseline definitions

Demographic data will be recorded during Visit 0 (Pre-Screening visit). All other baseline characteristics (medical history, concomitant diseases, previous and concomitant medications) will be recorded during Visit 1 (Screening).

For the primary efficacy endpoint, the baseline value is defined as the average of the FEV₁ pre-dose measurements on Visit 2 (45 min and 15 min pre-dose). In the same manner, for FVC the average of the FVC pre-dose measurements recorded at Visit 2 on Day 1 will be used as the baseline. *If one of the spirometry measurements at 45 min and 15 min pre-dose is not available, then the non-missing measurement will be taken as the pre-dose value. If no measurement is available, then the pre-dose value will be considered as missing.*

The baseline used in the analysis of PEF and diary data is the result recorded during the Run-in Period. Depending on the structure of the specific variable, this may be an average value, or a percentage.

Baseline ACQ-7 score is the ACQ score recorded at Visit 2, before randomization.

For vital signs, 12-lead ECG and urinary cortisol and creatinine, baseline values are those recorded pre-dose at Visit 2.

For laboratory the baseline values are the ones collected at Visit 1.

7.2 Baseline Characteristics and Derived Analysis Variables

The purpose of this section is to describe the calculation of all derived variables. All other variables that are obtained directly from the eCRF system with no derivation are not described in this section.

7.2.1 Demographic Characteristics

- Age of the subject will be calculated by the eCRF system based on the date of birth and date of Pre-Screening (Visit 0) entered into the system.

7.2.2 Asthma History and Pre-Study Smoking Habits

- The time since first Asthma diagnosis (months) will be calculated as:
(Visit 1 - the date of first diagnosis)/30.4375.
- Age at First Asthma Diagnosis (years) will be calculated in SAS using the following formula: floor(yrdif(date of birth, date of first diagnosis, 'AGE')).
- The Duration of Smoking (years) will be calculated using the start/stop date of smoking as: (smoking stop date - smoking start date + 1)/365.25

Only the month and the year (not the day) is recorded on the eCRF for Date of first diagnosis and smoking start/stop date. The first day of the month will be assumed for these dates in order to calculate time duration variables.

In order to calculate the duration, the following rules will be applied for the partial dates: if the month is missing, January 1st will be assumed. When the start date is completely missing, the time duration variable will not be calculated.

7.2.3 Screening and Baseline Subject Characteristics

- Asthma Control Questionnaire (ACQ) score at Visit 1 and Visit 2 will be calculated within the eCRF.
- Medical/Surgical History and Concomitant Diseases will be collected during Visit 1. All conditions that are not indicated as ongoing will be considered as medical/surgical history, while conditions indicated as ongoing will be considered as concomitant diseases.
- Body Mass Index (kg/m^2) is collected at Visit 1 and calculated as $\text{Weight (kg)} / [\text{Height (m)}]^2$
- Use of rescue medication, asthma symptoms, and PEF are collected twice daily during the run-in period via subject eDiary. For derivation of summary statistics for rescue medication, asthma symptoms, and PEF during the run-in period, a minimum of 7 days with some non-missing data is required.
- Spirometry will be performed prior to and following bronchodilator at Visit 1 and prior to dosing at Visit 2.

7.2.4 Spirometry and ACQ at Screening

At Visit 1, if documentation of airway reversibility within 1 year prior to V1 is not available, airway reversibility will be assessed with spirometry in triplicate maneuvers before and within 30 minutes after administration of 4 separate doses of albuterol HFA (90 μg /actuation, total dose 360 μg) at 30-sec intervals. The reversibility parameters (i.e., ΔFEV_1 (mL), % ΔFEV_1) will be calculated in the eCRF. Historical reversibility will be presented separately from reversibility calculated during the study.

If the reversibility test of Visit 1 is repeated in a (pre-randomization) rescheduled visit (called Visit 1.1 in the eCRF), then all spirometry values of the rescheduled visit will be used for the analysis. The same approach will be applied to ACQ.

7.2.5 Previous and Concomitant Medications

Medications will be split into four categories:

- **Previous medications** are those medications started and stopped prior to the initial exposure to the study drug (medication start date < date of first study drug intake and medication stop date \leq date of first study drug intake).
- **Maintained medications** are all medications started before initial exposure to the study drug and ongoing at initial exposure to the study drug (medication start date < date of first study drug intake and medication stop date > date of first study drug intake).
- **Concomitant medications** are all medications started during the treatment period (date of first study drug intake \leq medication start date < date of last study drug intake).

- **Post-treatment medications** are all medications started on or after the last dose of study drug (medication start date \geq date of last study drug intake).

In case of missing or incomplete dates not directly allowing allocation to any of the four categories of medications, a worst-case allocation will be performed according to the available parts of the start and the stop dates. The medications will be allocated to the first category allowed by the available data, according to the following order:

1. concomitant medication;
2. maintained medication;
3. post-treatment medication;
4. prior medication.

Information on previous and concomitant medications is retrieved from the ‘Prior and Concomitant medications’ eCRF page.

In the analyses, some Preferred Names will be presented under a common name in order to improve the readability of the tables. The common name will be presented instead of the associated preferred names in the tables and the frequency distribution will be evaluated considering the common names (e.g., if one patient took two medications with different Preferred Names but the same common name, he/she will be counted only once under the common name in the tables). In the listing, the Preferred Names will not be replaced by the common names. The common name and the associated Preferred Names considered in the analyses are summarised in the table below.

| Common name | Preferred Names |
|----------------------------|-----------------------------------------------------------------------------------|
| “BUDESONIDE” | “BUDESONIDE” |
| “FLUTICASONE W/SALMETEROL” | “FLUTICASONE W/SALMETEROL” “SERETIDE” “FLUTICASONE PROPIONATE W/SALMETEROL” |
| “BUDESONIDE W/FORMOTEROL” | “BUDESONIDE W/FORMOTEROL” “BUDESONIDE W/FORMOTEROL FUMARATE” |
| “FLUTICASONE W/VILANTEROL” | “BREO ELLIPTA” “FLUTICASONE FUROATE W/VILANTEROL” |
| “MOMETASONE W/FORMOTEROL” | “DULERA” |
| “IPRATROPIUM W/SALBUTAMOL” | “COMBIVENT” “IPRATROPIUM W/SALBUTAMOL” |

7.2.6 Previous and Concomitant Procedures

Procedures will be split into two categories:

- **Previous procedures** are all procedures started and stopped prior to the treatment period (procedures start date $<$ date of first study drug intake and procedures stop date \leq date of first study drug intake).

- **Maintained procedures** are all procedures started before initial exposure to the study drug and ongoing at initial exposure to the study drug (procedures start date < date of first study drug intake and procedures stop date > date of date of first study drug intake).
- **Concomitant procedures** are all procedures started during the treatment period (date of first study drug intake <= procedures start date < date of last study drug intake).
- **Post-treatment procedures** are all procedures started on or after the end of randomized period (procedures start date >= date of last study drug intake).

In case of missing or incomplete dates not directly allowing allocation to the any of the four categories of procedures, a worst-case allocation will be performed according to the available parts of the start and the stop dates. The procedures will be allocated to the first category allowed by the available data, according to the following order:

1. concomitant procedures;
2. maintained procedures;
3. post-treatment procedures;
4. previous procedures.

Information on concomitant procedures is retrieved from the ‘Concomitant procedures’ eCRF page. Procedures will be listed only.

7.2.7 Treatment Exposure and Compliance – Background Medication

Run-In Period / Exposure and Compliance

At Visit 1, the investigator will prescribe the subject QVAR[®] 40µg or QVAR[®] 80µg 1-2 puffs bid (80 – 320µg/d) at an equipotent dose to replace the subject’s prior ICS. The 1st dose of QVAR[®] will be administered on-site at V1. Subsequently, the subject will be instructed to discontinue the use of any other ICS for the duration of the study. The background QVAR[®] medication should not be taken in the morning before coming to the clinic (at V1.1 and V2) and will be discontinued at V2. This treatment regimen should remain stable for the entire run-in period.

The Run-In Period starts at Visit 1 and runs through the day before Day 1 (Day -1). Note that the morning diary questions refer to the previous evening. Therefore, assessments related to the evening of the day before Day 1 (Day -1) will be answered in the diary on the morning of Day 1. Exposure during the Run-in Period are based on actual dosing date/times and not visit dates. Exposure will be calculated using the:

date of last dose of the Run-in Period – date of first dose of the Run-in Period + 1 day.

Compliance to background medication during the run-in period is based on eCRF and diary data. If visit 1 information is available from both eCRF and diaries, data entered by the investigator in the eCRF will be taken into account.

The evaluation of compliance will be based on the number of puffs following the formula presented below:

$$\frac{\text{Total number of administered puffs (as recorded in the Subject Diary and Background Medication Administration eCRF page)}}{\text{Total number of scheduled puffs}} \times 100\%$$

The total number of **scheduled puffs per day** is the sum of the ‘Number of puffs the subject has been instructed to take: ‘Morning puffs’ plus ‘Evening puffs’ as recorded on the Screening ‘Background Medication Administration for Asthma’ eCRF page.

The total scheduled number of puffs during the Run-in Period is defined as:

$$[\text{Run-in period duration (days)}] \times [\text{scheduled number of puffs per day}]$$

The approach above defined for the calculation of compliance assumes no intake of the background medication in case of missing data.

The compliance will be summarized using the following categories:

- Treatment compliance < 65%
- $65\% \leq \text{Treatment compliance} \leq 135\%$
- Treatment compliance > 135%.

and the following categories:

- [0%-10%]
- (10%-20%]
- (20%-30%]
- (30%-40%]
- (40%-50%]
- (50%-60%]
- (60%-70%]
- (70%-80%]
- (80%-90%]
- (90%-100%]
- (100%-110%]
- (110%-120%]
- (120%-130%]
- (130%-140%]
- >140%

7.2.8 Treatment Exposure and Compliance - Study Drug Administration

The actual date and time of study drug administration will be used to calculate exposure. The following dosing schedule will be followed for the 8-week treatment period; study drug will be administered twice-a-day (in the morning and in the evening), with the last dose taken the evening before Visit 4. Note that the morning diary questions refer to the previous evening. Therefore, assessments related to the evening of the day before Day 1 (Day -1) will be answered in the diary on the morning of Day 1.

For **Treatment Arms A, B, C and D** dosing schedule is:

Morning administration (between 8-10 am):

- One inhalation from the canister labeled 1
- One inhalation from the canister labeled 2
- One inhalation from the canister labeled 3
- One inhalation from the canister labeled 4

Evening administration (between 8-10 pm):

One inhalation from the canister labeled 1
One inhalation from the canister labeled 2
One inhalation from the canister labeled 3
One inhalation from the canister labeled 4

For **Treatment Arm E** dosing schedule is:

Morning administration (between 8-10 am):

Two inhalations from QVAR[®] 80 µg pMDI

Evening administration (between 8-10 pm):

Two inhalations from QVAR[®] 80 µg pMDI

If the settings in the electronic diary are incorrect at randomization for a subject (e.g., Run-in period settings are applied during the treatment period), such that data is not collected for study drug administration during some days during the treatment period, then compliance and exposure will not be calculated for that subject for sessions (morning/evening) on which the settings were incorrect. Instead, compliance will be calculated based on sessions during which the settings were correct. The information recorded at the study clinic will always be considered in the calculation (i.e. day will be considered in calculation if exposure is recorded at clinic in a day where diary has an incorrect setting). For these subjects, the duration of the treatment period (as used for calculation of scheduled puffs) will be reduced by the number of days during which the settings were incorrect. In other words, days with incorrect diary settings will be excluded from the numerator and denominator of the compliance calculation for these subjects. If the diary settings were incorrect during the entire treatment period, then compliance and exposure will not be calculated for the subject. To be considered as incorrect, diary data should be nonmissing and questions answered consistent with a different period. For example (I=incorrect questions, C=correct questions, M=missing data):

- Day 1: I
- Day 2: I
- Day 3: M
- Day 4: M
- Day 5: C.

In this case, the last “incorrect day” is Day 2.

The same approach will be applied to sessions for which any questions related to the wrong treatment arm (ABCD vs E) were asked, that will not be used in the calculation of compliance. Notably, these sessions will not contribute to the numerator (number of administered puffs) or the denominator (number of scheduled puffs). For these subjects, the total number of scheduled puffs will be based on treatment exposure days, excluding sessions with any incorrect diary questions. This includes sessions where duplicate questions were answered. In these cases, all data at the session is considered unreliable, so even the correct questions will be excluded.

The dosing occasions for study drug are expected to be taken during the visit dates, however exposure and compliance are based on actual dosing date/times and not visit dates. See Section 7.1 for the definition of the study periods and period durations (days).

For the calculation of the number of administered and scheduled doses, the dosing occasions from the first to the last study drug intake will be taken into account (i.e. any study drug recorded in the Subject Diary after the date of last dose (as recorded on the ‘Study Termination’ eCRF page) will be ignored for study drug compliance calculations).

If Date of last intake of study drug (as recorded on the ‘Study Termination’ eCRF page) is missing or partially missing, dosing occasions of the study drug recorded in the diaries or at the clinic will be taken into account until the ‘last randomized study drug intake’ as defined in Section 7.1.

Exposure will be calculated as the Date of last intake of study drug – date of first intake of study drug + 1 day.

The evaluation of compliance is done using the following formula:

$$\frac{\text{Total number of administered puffs (as recorded in the Subject Diary and Study Drug Administration at the Clinic eCRF page)}}{\text{Total number of scheduled puffs}} \times 100\%$$

The **total number of administered puffs** will be calculated by adding up the number of puffs taken during the Treatment period, as recorded in the Subject Diary and ‘Study Drug Administration at the Clinic’ eCRF page.

Information on study drug intake is retrieved from the eCRF (on visit days) and subject diaries. If on a visit day information (morning or evening session) is available from both eCRF and diaries, data entered by the investigator in the eCRF will be taken into account.

It should be noted that 4 puffs (for Arms A, B, C, and D) or 2 puffs (for Arm E) should be taken twice a day during the Treatment period (from the morning of Day 1 (V2) until the evening of the day before V4). No study treatment is to be administered on the morning of Visit 4.

The approach above defined for the calculation of compliance assumes no intake of the study drug in case of missing data.

The total number of scheduled puffs is defined during the treatment period as:

- Scheduled number of puffs = Treatment exposure (days) x [scheduled puffs per day].
- If a subject is randomized into the study and discontinues the same day, then the subject was included in the study for 1 day. Hence, the expected number of puffs would be 1 day * [scheduled puffs per day].

Any level of compliance with study treatment in the interval [65%; 135%] is considered as satisfactory after randomization. Therefore, the following categories will be discerned for Treatment Period:

- Treatment compliance < 65%
- 65% ≤ Treatment compliance ≤ 135%
- Treatment compliance > 135%.

The compliance will also be summarized as per following categories:

- [0%-10%]
- (10%-20%]
- (20%-30%]
- (30%-40%]
- (40%-50%]
- (50%-60%]
- (60%-70%]
- (70%-80%]
- (80%-90%]
- (90%-100%]
- (100%-110%]
- (110%-120%]
- (120%-130%]
- (130%-140%]
- >140%

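### SAP 7.2.8 withholds study-drug exposure when the diary was misconfigured throughout treatment, although exposure comes by default from eCRF dates

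*SAP*

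**What the plan says.** SAP 7.2.8 deals with diaries that ran the wrong questions after randomization, for example run-in settings during treatment. It has two rules.

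- **Some sessions affected:** "then compliance and exposure will not be calculated for that subject for sessions (morning/evening) on which the settings were incorrect". Compliance then rests on the sessions with correct settings.
- **Whole treatment period affected:** "If the diary settings were incorrect during the entire treatment period, then compliance and exposure will not be calculated for the subject".

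Later in the same section the definition is: "Exposure will be calculated as the Date of last intake of study drug – date of first intake of study drug + 1 day".

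SAP 7.1 gives the sources of the two dates.

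- **First intake:** "Only CRF data will be considered for the date of first randomized study drug intake". The clinic dosing date and time are mandatory: "no missing or partial data can be accepted".
- **Last intake, by default:** "Date of last randomized study drug intake is derived as 'Date/Time of last intake of study drug' variable collected on the 'Study Termination form' eCRF". Where that entry is missing or partial, the later of the last diary date and the last clinic dosing date is used.

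SAP 10.5.2 summarizes exposure in the ITT and Safety populations (Tables 14.1.11.1 and 14.1.11.2).

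**The concern.** The whole-period rule sets to missing a quantity that the diary setting does not normally affect. An affected subject stays in the ITT and Safety populations, and any adverse events stay in the safety tables, but the subject contributes nothing to the exposure summary. The exposure and adverse event tables for an arm would then describe different numbers of treated subjects, for no reason connected with what is known about dosing.

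The session-level sentence raises a second, smaller problem. A first-to-last-date duration has no sessions to withhold, so a programmer has to guess what the instruction means for exposure. One might leave the duration whole and another might subtract the affected days. The SAP does not say which is intended.

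**Working it through.** The plan states no figure on this point, so there is none to reproduce. The check follows the derivation from its inputs to the output tables.

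**1. Does the diary enter exposure?**

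| Quantity | Formula (SAP 7.2.8) | Inputs | Diary needed? |
|---|---|---|---|
| Compliance | administered puffs / scheduled puffs × 100 | diary puffs plus clinic dosing page | yes |
| Exposure | last date − first date + 1 | CRF first date; Study Termination eCRF last date | not by default |

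No puff or session count enters exposure.

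**2. Value for a completer on schedule with no usable diary.** Visit 2 is Day 1. Visit 4 is 56 days later, on Day 57. SAP 7.2.8 puts the last dose on the evening before Visit 4, Day 56.

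Exposure = 56 − 1 + 1 = 56 days.

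The protocol (7.1.3 and 7.1.4) allows ±2 days on each 4-week interval. If both run short, Visit 4 comes 26 + 26 = 52 days after Visit 2 and exposure is 52 days. If both run long, it comes 30 + 30 = 60 days after and exposure is 60 days. Under the whole-period rule the value in each case is missing.

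**3. Value if the eCRF last date is also missing.** The fallback takes the later of the diary and clinic dates. With no usable diary date, the clinic date remains.

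- Last clinic dose at Visit 3 on schedule (Day 29): 29 − 1 + 1 = 29 days (27 to 31 with the ±2-day window).
- Dosed in clinic only at Visit 2: 1 − 1 + 1 = 1 day.

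These are lower bounds, since dosing at home may have continued, but a value exists.

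**4. Partial misconfiguration.** SAP 7.2.8 shortens the treatment duration by the affected days when it computes scheduled puffs. It also sets scheduled puffs equal to treatment exposure in days times puffs per day. With d affected days for a completer on schedule, the compliance denominator uses 56 − d days, while the date formula still gives an exposure of 56 days. Both quantities can be read as treatment exposure, so one can overwrite the other in the program.

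**5. Where it shows.** SAP 8.1 lists the summary statistics as n, mean, SD, confidence interval, minimum, median and maximum. An affected subject lowers n in both exposure tables. SAP 10.7.1 reports adverse events as event counts and as numbers and percentages of subjects in the Safety population, so those tables keep the subject.

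**The case against.** The best defence is that the rule is narrow and mostly about compliance. A setting counts as incorrect only if the diary holds answers belonging to a different period, and the whole-period rule needs that to last throughout treatment. The protocol has sites check recorded data regularly through a portal (7.2.12) and look at the diary portal again at Visit 3 (7.1.4). These checks are aimed at compliance and correct use, so they do not guarantee that a wrong setting is found. They do make an eight-week error unlikely. That stands, and it keeps the point small.

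The defence is also fair on the session-level sentence. The same paragraph uses the word exposure for a dosing record made at the clinic, ties the shortened duration to scheduled puffs, and restates the rule as removing days from the numerator and denominator of compliance. A reader might infer that this sentence also removes subjects from the exposure table. The text does not support that; the sentence is ambiguous, and only the whole-period sentence removes anyone.

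Other stronger readings also go too far.

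- **Mean exposure is understated.** Leaving subjects out moves the mean either way, depending on whether they were treated for a long or a short time.
- **Adverse event rates are distorted.** No exposure-adjusted rate is planned.
- **A sum of subject-days is lost from the report.** No such total is listed among the summary statistics, and the documents give no misconfiguration rate from which to estimate one.
- **Exposure never needs the diary.** It may, when the eCRF last date is missing or partial.

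The reported n would show the shortfall, and the dosing and disposition listings and the time-to-discontinuation plot would remain. None of this explains why a computable value should be discarded.

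**Conclusion.** The point holds for subjects whose diary settings were wrong for the entire treatment period. For them SAP 7.2.8 suppresses a value that its own formula and the section 7.1 dates supply: 56 days for a completer on schedule, less for someone who withdrew early. Both the ITT and the Safety exposure tables are affected. For partly affected subjects the session-level wording needs clarifying, but it does not clearly remove anyone.

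The size is one missing exposure value per affected subject. The number of such subjects is not given, may be small and could be zero. No efficacy result and no adverse event count or percentage changes. The conclusion assumes that the Study Termination page normally carries the last intake date; where it does not, the fallback still gives a value, possibly too short. This is a minor correction, worth making because it costs almost nothing.

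**What to change.** In SAP 7.2.8:

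1. Delete the words *and exposure* from both sentences on incorrect diary settings, so that the rule applies to compliance only.
2. State that exposure is derived for every treated subject from the first and last intake dates of section 7.1, including the fallback for a missing or partial last date. Restricting it to eCRF dates alone would drop that fallback and open a new gap. Flag subjects whose last date came from the fallback.
3. Give the shortened duration used for scheduled puffs its own name, distinct from exposure, so that it cannot overwrite the exposure variable.

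The change applies to Tables 14.1.11.1 and 14.1.11.2 and to the exposure listing. It costs a few words of text, one variable name, one program condition and the fallback flag. No new data are needed.
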